#### 3.1.8 Bayesian Analysis Results

For the Bayesian analysis, the following results will be provided as appropriate:

- the posterior probability for non-inferiority
- the posterior medians by treatment arm and their 95% credible intervals
- the posterior median of treatment difference (PE\_ACURATE minus PE\_Control) and it's 95% credible intervals
- the highest posterior density (HPD) intervals and the equal-tail posterior intervals for the estimated parameters
- other data derived from the posterior distribution, such as: model fitting statistics, posterior mean, and graphic presentation of the posterior distributions of the parameters

#### 3.1.9 Bayesian Design Operating Characteristics

#### 3.1.9.1 Simulation setup

Piecewise exponential model:

1) Time intervals follow the actual follow-up visits defined in the protocol, which are the intervals as 0 - 30 days, 31 - 180 days, and 181 - 365 days post randomization for the ITT analysis.

2) Hazard rate within each time interval is constant. The hazard rates may be different between different intervals. The following is the hazard function defined by different treatment groups:

 $h_{j}(t) = \begin{cases} \lambda_{j,1}, & 0 \le t \le 30 \ days \\ \lambda_{j,2}, & 31 \le t \le 180 \ days \\ \lambda_{j,3}, & 181 \le t \le 365 \ days \end{cases}$ 

Where j=1 or 2 for the test and the control groups within each risk stratum, respectively.

3) SAS Programming Software and the Procedure PROC MCMC are used for simulation and the Bayesian analyses.

Note: the piecewise exponential models are constructed by risk stratum, treatment group, and time interval. The parameters to be estimated are specified in Section 3.1.5.2 Table 1.

Simulation parameters

- 1) Proper and reasonably non-informative prior Gamma (shape=0.0001, inverse-scale=0.0001)
- 2) Assumption of number of subjects available for each time interval at the time of the interim analysis by risk stratum for each treatment group (total N=750 per treatment group) (Table 2).

Risk Stratum	30-Day	6-Month	1-Year
E/HR	262	241	194
IR	225	225	221
LR	262	223	115

Table 2. Available Data for Simulations at Interim for each treatment group

- 3) Expected rate for the Control (22.3%)
- 4) Expected rate for the Test (30.3% for alpha, 22.3% for the power).
- 5) Hazard rates assumptions by the time intervals as following (Table 3):

 Table 3. Cases for the Relationship between Lambdas for Simulations

Hazard assumptions*	λ2	λ3	
Case 1	0.4*λ1	0.3*λ1	
Case 2	0.3*λ1	0.2*λ1	
Case 3	0.3*λ1	0.1*λ1	
Case 4	0.2*λ1	0.2*λ1	

\*The assumptions are estimated based on historical data for event rates at 30-day, 6month, and 1-year (Table 4).

#### Form/Template 90702621 Rev/Ver AF ACURATE IDE SAP 92400558, Rev/Ver I Page 32 of 64

Clinical Study	Device	Risk Profile	Available Event	Event rate by time 30d vs 6m vs 12m	Estimated Lambdas (λ1, λ2, λ3)
Partner 2B	SAPIEN XT	Extreme	death/major stroke/rehosp	17% vs 28% vs 37%	λ2=0.15*λ1 λ3=0.12*λ1
CoreValve ER	Corevalve	Extreme	death/major stroke	10% vs 19% vs 26%	λ2=0.19*λ1 λ3=0.14*λ1
Partner 1A	SAPIEN	High	death/major stroke	7% vs 18% vs 26%	λ2=0.33*λ1 λ3=0.23*λ1
CoreValve HR	CoreValve	High	death/major stroke	5.2% vs 11.5% vs 16.3%	λ2=0.25*λ1 λ3=0.17*λ1
CoreValve IR	CoreValve	Intermediate	death/major stroke	2.8% vs 6.0% vs 8.1%	λ2=0.23*λ1 λ3=0.13*λ1
Evolut LR	CV 31mm, Evolut R/Pro	Low	death/major stroke	0.8% vs 1.9% vs 2.9%	$\lambda 2=0.27*\lambda 1$ $\lambda 3=0.21*\lambda 1$
PARTNER 3	Sapien 3	Low	death/stroke/rehosp	4.2% vs 6.5% vs 8.5%	$\lambda 2=0.11*\lambda 1$ $\lambda 3=0.08*\lambda 1$
					λ1>λ2>λ3
				Range for λ2 related to λ1 Mean [min, max]	0.22 [0.11, 0.33] of λ1
				Range for λ3 related to λ1 Mean [min, max]	0.15 [0.08, 0.23] of λ1

Table 4. Historical Event Rate (Observed or Estimated) by Time Intervals

6) Run 2000 trials and draw 3,000 samples for each trial.

7) Seeds used for piecewise exponential models is 12345.

8) Sensitivity analysis by time intervals.

The purpose for the sensitivity analyses is for evaluate the robustness of the prespecified piecewise exponential models in terms of type I errors. The following time interval will be used for constructing the sample data for simulations

Case 1: [0, 7], [8, 30], [31, 365]

Case 2: [0, 7], [8, 90], [91, 365]

Case 3: [0, 90], [91, 180], [181, 365]

Case 4: [0, 180], [181, 270], [271, 365]

For each case, the sample data distribution will follow these time intervals with constant hazard rate within each interval. However, the analysis using the piecewise exponential model will follow the prespecified time intervals ([0, 30], [31, 180], [181, 365]) for the hypothesis test of the primary endpoint. The sensitivity analysis for type I error will be evaluated based on the piecewise exponential models with pre-specified fixed time intervals ([0, 30], [181, 365]) and on the sample data that are not following the same distribution (for example in Case 1: data with constant hazard rates within [0, 7], [8, 30], [31, 365]).

#### 3.1.9.2 Summary of Simulation Results

The type I error is simulated when the observed Test rate minus the observed Control rate is equal to the prespecified margin 8.0% while the observed Control rate is as the expected 22.3%. The power is simulated when the observed Test Rate is equal to the observed Control rate as the expected 22.3%.

After considering all simulation results from different simulation parameters specified in Section 3.1.9, we choose  $\xi = 97.5\%$  as the threshold for the posterior probability threshold for testing treatment difference of PE ACURATE minus PE Control for the noninferiority test. Given this threshold, the simulations show that the type I error is reasonably controlled at 2.5% for the interim and final analyses. While in a few cases, the type I errors are slightly greater than 2.5% due to the simulation random error and the total number of models (the eighteen models for each trials), they are well within the Exact 95% confidence interval [1.9%, 3.3%] of the desired 2.5% Type I error for the 2000 samples. For the expected hazards estimated from other studies when  $\lambda 2=0.3*\lambda 1$ and  $\lambda 3=0.2*\lambda 1$ , the type I errors are less than 2.5% and within the confidence interval of the 2.5% for both the interim and the final. As the results show, the type I error results are consistent across different scenarios. No evidence shows that these numbers are statistical different from the 2.5%, thus Type I error is reasonably controlled (Table 5). Considering variabilities from time to event sample data and each piecewise exponential model (from 18 models) with the process of the Bayesian posterior sampling for all the parameters, and combining with robustness of the simulation results, it is believed that piecewise exponential models will model the data well. The selection of the threshold for the hypothesis test is reasonable and will provide a robust evaluation on the primary endpoint result for the study.

Simulation Parameters				Rate minus				
Test Rate	Control Rate	Hazard Rate	Time Interval*	Time	ξ=97.1%	ξ=97.3%	ξ=97.5%	ξ=97.7%
30.30%	22.3%	λ2=0.4*λ1 λ3=0.3*λ1	[0, 30] [31, 180] [181,365]	Interim	2.70%	2.55%	2.45%	2.30%
				Final	0.75%	0.65%	0.55%	0.60%
30.30%	22.3%	λ2=0.3*λ1 λ3=0.2*λ1	[0, 30] [31, 180] [181,365]	Interim	2.80%	2.45%	2.10%	2.00%
				Final	1.05%	0.85%	0.95%	1.05%
30.30%	22.3%	λ2=0.3*λ1 λ3=0.1*λ1	[0, 30] [31, 180] [181,365]	Interim	2.45%	2.30%	2.25%	2.25%
				Final	0.70%	0.75%	0.65%	0.50%
30.30%	22.3%	λ2=0.2*λ1 λ3=0.2*λ1	[0, 30] [31, 180] [181,365]	Interim	2.85%	2.65%	2.45%	2.30%
				Final	0.85%	0.75%	0.85%	0.80%

Table 5. Simulation Results for Type I Errors Simulated type I error

\*Time intervals are used for both the sample data and the models for the simulations.

The sensitivity analyses are performed to evaluate the robustness of the prespecified piecewise exponential models. The sample data constructed from piecewise exponential distribution based on different time intervals (specified 3.1.9.1) are used to fit the

prespecified piecewise exponential with the prespecified time intervals [0,30], [31,180], [181,365]. The results of the sensitivity analysis for type I error by time interval are shown in Table 6. The results show the type I errors are similar and consistent to the results in Table 5 and reasonably controlled around 2.5%. The simulation results for the type I errors show that the prespecified piecewise exponential models are robust even when constant hazard distributions for the sample data deviate from the prespecified models.

	1 4010 0.	Sensitivity	Analysis for	Type TEI	101 Uy 111		ai		
Simulatio	n Parameters			Chance of the Posterior Probability for Test Rate minus Control Rate <8% is greater than ξ					
Test Rate	Control Rate	Hazard Rate	Time Interval*	Time	ξ=97.1%	ξ=97.3%	ξ=97.5%	ξ=97.7%	
		22 0 4*2 1	[0, 7]	Interim	2.95%	2.75%	2.45%	2.15%	
30.30%	22.3%	$\lambda 2=0.4*\lambda 1$ $\lambda 3=0.2*\lambda 1$	[8, 30] [31,365]	Final	1.20%	0.95%	1.00%	1.10%	
30.30%	22.3%	$\lambda 2=0.3*\lambda 1 \ \lambda 3=0.1*\lambda 1$	[0, 7] [8, 30] [31,365]	Interim	2.20%	2.15%	2.00%	1.85%	
				Final	1.40%	1.15%	1.00%	1.00%	
30.30%	22.3%	$\lambda 2=0.4*\lambda 1 \ \lambda 3=0.2*\lambda 1$	[0, 7] [8, 90] [91,365]	Interim	3.00%	2.75%	2.60%	2.40%	
				Final	1.35%	1.30%	1.25%	1.20%	
30.30%	22.3%	$\lambda 2=0.3*\lambda 1 \ \lambda 3=0.1*\lambda 1$	[0, 7] [8, 90] [91,365]	Interim	3.10%	3.00%	2.70%	2.40%	
				Final	0.90%	0.80%	0.70%	0.60%	
30.30%	22.3%	$\lambda 2=0.4*\lambda 1 \ \lambda 3=0.2*\lambda 1$	[0, 90] [91, 180] [181,365]	Interim	2.75%	2.70%	2.50%	2.35%	
				Final	0.95%	0.85%	0.90%	0.85%	
30.30%	22.3%	$\lambda 2=0.3*\lambda 1 \ \lambda 3=0.1*\lambda 1$	[0, 90] [91, 180] [181,365]	Interim	2.30%	2.15%	2.00%	1.80%	
				Final	0.90%	0.80%	0.80%	0.70%	
30.30%	22.3%	$\lambda 2=0.4*\lambda 1$ $\lambda 3=0.2*\lambda 1$	[0, 180] [181, 270] [181,365]	Interim	3.15%	2.85%	2.65%	2.35%	
				Final	0.75%	0.80%	0.85%	0.80%	
				Interim	2.40%	2.30%	2.15%	2.10%	
30.30%	22.3%	λ2=0.3*λ1 λ3=0.1*λ1	[0, 180] [181, 270] [271,365]	Final	0.95%	0.90%	0.90%	0.90%	

Table 6. Sensitivity Analysis for Type I Error by Time Interval

\* Intervals used for creating sample data. The models used the intervals: [0,30], [31, 180], [181, 365] as prespecified for the primary endpoint analysis.

The study power (1-minus type II error) is more than 90% at the interim or the final analysis of the primary endpoint from the simulation results as shown in Table 6. The study is sufficiently powered for the primary endpoint analysis.

	Simulation	Chance of the Posterior Probability for Test Rate minus Control Rate <8% is greater than ξ						
Test Rate	Control Rate	Hazard Rate	Time Interval	Time	ξ=97.1%	ξ=97.3%	ξ=97.5%	ξ=97.7%
	22.3%	$\lambda 2=0.3*\lambda 1 \ \lambda 3=0.2*\lambda 1$	[0, 30] [31, 180] [181,365]	Interim	95.65%	95.45%	95.15%	94.70%
22.30%				Final	97.50%	97.40%	97.05%	96.85%

Table 6. Simulation Results for Study Power

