11.1.1.2. Sample Size Parameters for the Primary Endpoint - Main Randomized Cohort

Although the primary endpoint analysis is performed using the Bayesian method, the sample size calculation for the randomized cohort (see *Note 2* below) is based on a standard non-inferiority two-sample test approach. The sample size calculation for the primary endpoint is based on the following assumptions.

- Expected rate for both arms = 22.3% (based on a weighted average of TAVR data^{19,22,28-30,34,41,46,51,82}; see *Note 3* below)
- Non-inferiority margin (Δ) = 8.0% (36% relative to expected rate)
- Test significance level (α) = 0.025 (1-sided) (see Note 4 below)
- Test (ACURATE): Control ratio = 1:1
- Power $(1 \text{ minus } \beta) > 90\%$
- Expected rate of attrition = 5%
- Total sample size = 1500 (750 per group)
- Number of evaluable subjects per group = 712
- Analyses: One administrative, one formal interim, one final (see *Note 5* and *Note 6* below)

Note 2: The Pocock-type method⁸³ is used for sample size calculations. The statistical software $EAST^{\circledast} 6.5^{84}$ is used for the sample size calculations.

Note 3: The estimated proportions of subjects in the Main Randomized Cohort by operative risk level are 10% extreme risk, 25% high risk, 30% intermediate risk, and 35% low risk.

Note 4: A statistically equivalent posterior probability threshold for the Bayesian analysis is empirically chosen through extensive simulations and is pre-specified in the Statistical Analysis Plan (SAP).

Note 5: The administrative interim analysis will be conducted when the first 350 Main Randomized Cohort subjects have completed 1-year follow-up. The formal interim analysis will be carried out after enrollment in the Main Randomized Cohort is completed. This formal interim analysis will be conducted on the full N=1500 subject cohort of the Main Randomized Cohort after the first 1050 subjects in the Main Randomized Cohort have completed 1-year follow-up. The piecewise exponential model³⁰ based on outcomes among these subjects will be used to predict the 1-year results by treatment group for the remaining enrolled subjects. The Bayesian method will be used to perform the hypothesis testing on the combined data sets. A final analysis will be performed on all subjects with completed 1-year data if non-inferiority cannot be claimed at the formal interim analysis (see Section **11.1.1.3**).

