## 3.1.2 Sample Size

Although the primary endpoint analysis is performed using the Bayesian method, the sample size calculation for the Main Randomized Cohort is based on a standard non-inferiority two-sample test approach with one formal interim analysis planned. The sample size calculation for the primary endpoint is based on the following assumptions.

- Expected rate for both arms = 22.3% (based on a weighted average of TAVR data
- Non-inferiority margin ( $\Delta$ ) = 8.0% (36% relative to expected rate)
- Test significance level ( $\alpha$ ) = 0.025 (1-sided)
- Test (ACURATE): Control ratio = 1:1
- Power  $(1 \text{ minus } \beta) > 90\%$
- Expected rate of attrition = 5%
- Total sample size = 1500 (750 per group)
- Number of evaluable subjects per group = 712
- Analyses: One administrative, one formal interim, one final

The Pocock-type method is used during sample size calculations when 70% subjects reached 1-year follow-up at the formal interim analysis. The statistical software EAST® 6.5 is used for the sample size calculations.

The estimated proportions of subjects in the Main Randomized Cohort by operative risk level are 10% extreme risk, 25% high risk, 30% intermediate risk, and 35% low risk.

The formal interim analysis will be carried out after enrollment in the Main Randomized Cohort is completed. This formal interim analysis will be conducted on the full N=1500 subjects of the Main Randomized Cohort after first 1050 subjects in the Main Randomized Cohort have completed 1-year follow-up or at least 80% low risk subjects in the Main Randomized Cohort have completed 6-month follow-up, whichever comes later. The piecewise exponential models will be based on outcomes among these subjects who have completed 30-day, 6-month, or 1-year follow-ups. The results from the models will be used to estimate the 1-year results by treatment group through Bayesian posterior probabilities for the non-inferiority test. The final analysis for the primary endpoint will be performed on all subjects with completed 1-year data if non-inferiority cannot be claimed at the formal interim analysis.

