#### 3.1.3 Success Criteria

The Bayesian method is used to test the non-inferiority hypothesis of the primary endpoint. To establish that the ACURATE device is non-inferior to the Control, the results will need to meet the following equation:

 $Pr(H_1 | Data) > \xi$ 

where

- Pr(H1 | Data) is the posterior probability of H1 given the observed data at either the interim or the final analysis;
- H1 is the alternative hypothesis for non-inferiority: PE ACURATE minus PE Control  $< \Delta$ ;
- ξ is a prespecified threshold, which is empirically chosen through extensive simulations using the Bayesian approach for the noninferiority tests.

If non-inferiority has been declared at the formal interim analysis, the non-inferiority test will not be performed at the final analysis. If non-inferiority cannot be declared at this interim analysis, the non-inferiority test will be performed at the final analysis for all subjects using the Bayesian method with the same pre-specified threshold. The study will not stop for futility at the interim analysis.

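### Using the 97.5% threshold at both the interim and the final look gives an overall one-sided type I error of about 3% to 4%, not the 2.5% the SAP claims

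*SAP*

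**What the plan says.** Protocol 11.1.1.2 and SAP 3.1.2 set a one-sided alpha of 0.025, an expected rate of 22.3% in both arms and a margin of 8.0 points. Note 4 in the protocol section, attached to that alpha, says: "A statistically equivalent posterior probability threshold for the Bayesian analysis is empirically chosen through extensive simulations". For the sample size, SAP 3.1.2 says: "The Pocock-type method is used during sample size calculations when 70% subjects reached 1-year follow-up at the formal interim analysis".

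The decision rule is in SAP 3.1.3 and is repeated in 3.1.6. If the interim does not succeed, "the non-inferiority test will be performed at the final analysis for all subjects using the Bayesian method with the same pre-specified threshold". SAP 3.1.9.2 sets that threshold, ξ, at 97.5% and concludes: "Given this threshold, the simulations show that the type I error is reasonably controlled at 2.5% for the interim and final analyses". Of the sensitivity scenarios it adds: "The results show the type I errors are similar and consistent to the results in Table 5 and reasonably controlled around 2.5" per cent. Values slightly above 2.5% are attributed to simulation error, judged against an exact 95% interval of 1.9% to 3.3% for 2,000 simulated trials.

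**The concern.** Two chances to succeed at the same unadjusted cut-off must give a higher false-positive rate than one chance. The sample size calculation allowed for this through a Pocock-type adjustment, but the threshold has no such allowance: 97.5% is simply 1 − 0.025. The operating characteristics do not reveal the gap, because the Interim and Final rows are compared with 2.5% one at a time and no cumulative figure is given.

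At stake is the primary test behind the pivotal non-inferiority claim. The stated alpha is the chance of calling a device non-inferior when its event rate is a full 8 points worse, and that chance is understated.

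**Working it through.** **Inputs.** Null: 30.3% versus 22.3%. Threshold 97.5% at both looks. Interim counts per arm for the 30-day, 6-month and 1-year intervals (SAP Table 2): extreme/high risk 262/241/194, intermediate 225/225/221, low 262/223/115. Priors Gamma(0.0001, 0.0001). Interval lengths 31, 150 and 185 days. Risk weights 35/30/35% (SAP 3.1.5.4). 2,000 simulated trials.

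**Sample size reproduced.** n = (1.960 + 1.282)² × 2 × 0.223 × 0.777 / 0.08² = 569 per group for 90% power, and 704 for 95%. 712 / 0.95 = 749.5, so 750 enrolled. Lan-DeMets Pocock-type spending at 70% information spends 0.025 × ln(1 + (e − 1) × 0.7) = 0.0197 at the interim, leaves a nominal 0.0122 at the final, and gives 93.2% power with 712 per group. The sample size is sound, with an adjustment that the decision rule lacks.

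**What the Final rows are.** The SAP does not label them, so this is inferred from the numbers:

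1. At 97.5% they are 0.55% to 1.25%. Each is below its interim value, so they are not cumulative. A stand-alone test at 97.5% with a vague prior has an error of about 2.5%, so they are not that either.
2. Some rise as the threshold tightens: 0.85%, 0.95%, 1.05% at 97.3/97.5/97.7% (Table 5, λ2 = 0.3λ1 and λ3 = 0.2λ1), and 0.95%, 1.00%, 1.10% (first row of the sensitivity Table 6). On the same simulated trials a stand-alone or cumulative rate cannot rise. An increment can, because trials that no longer pass at the interim may pass at the final.
3. Every entry is a multiple of 0.05% = 1/2,000, so the denominator is all trials and the two rows can be added.

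**Overall error from the SAP's tables at 97.5%.**

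| Table | Interim + Final (%) | Overall (%) |
|---|---|---|
| 5 | 2.45 + 0.55 | 3.00 |
| 5 | 2.10 + 0.95 | 3.05 |
| 5 | 2.25 + 0.65 | 2.90 |
| 5 | 2.45 + 0.85 | 3.30 |
| 6 | 2.45 + 1.00 | 3.45 |
| 6 | 2.00 + 1.00 | 3.00 |
| 6 | 2.60 + 1.25 | 3.85 |
| 6 | 2.70 + 0.70 | 3.40 |
| 6 | 2.50 + 0.90 | 3.40 |
| 6 | 2.00 + 0.80 | 2.80 |
| 6 | 2.65 + 0.85 | 3.50 |
| 6 | 2.15 + 0.90 | 3.05 |

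The mean is 38.70 / 12 = 3.2%. All 12 exceed 2.5%; five exceed 3.3% and one equals it. At 97.7%, the strictest threshold tabulated, 11 of 12 still exceed 2.5% and the other equals it (1.80 + 0.70).

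**Re-simulation.** Posteriors are Gamma(0.0001 + events, 0.0001 + exposure), and each stratum rate is 1 − exp(−(31λ1 + 150λ2 + 185λ3)). The SAP does not give the stratum event rates used in its simulations. I assumed equal rates and, alternatively, rates in proportion 35/22/9.85.

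| Posterior method, trials per scenario | Interim | Final alone | Increment | Overall |
|---|---|---|---|---|
| Normal approximation, 60,000 | 2.5% | 2.3–2.6% | 0.8–1.1% | 3.35–3.64% |
| Gamma draws, 20,000 | 2.4–2.7% | 2.5–2.7% | 1.0–1.1% | 3.55–3.74% |
| Gamma draws, 4,000 | 2.0–2.8% | 2.5–2.9% | 1.1–1.2% | 3.2–3.9% |

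**Analytic check.** Overall error = 1 − P(Z1 ≤ 1.96, Z2 ≤ 1.96), with correlation √t at information fraction t. This gives 3.78% at t = 0.7, 3.54% at 0.8 and 3.24% at 0.9.

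**The case against.** Several points on the other side have weight.

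- **The reading of Final is inferred.** The power table uses the same column heading, yet its Final value (97.05%, beside 95.15% at the interim) cannot be an increment, since the two add to more than 100%. So the tables use different bases and the sponsor should confirm. For type I error, no other reading fits the numbers.
- **No overall 2.5% is printed.** The SAP's sentence is true of each look taken alone. But the plan states a one-sided 0.025 and promises an equivalent threshold, and the rule as a whole does not deliver it.
- **The Monte Carlo breaches are all in the sensitivity table.** The four Table 5 sums (2.90% to 3.30%) lie within 1.9% to 3.3%. That is right for single rows. It does not explain all 12 falling on the same side, or re-simulations with ten or more times as many trials.
- **70% is not the information in the interim model.** Table 2 keeps 749 of 750 subjects per arm for 30 days, 689 (92%) for 6 months and 530 (71%) for 1 year, and the simulated information was about 79% to 89%. This lowers the analytic figure to roughly 3.2% to 3.6%, still above 2.5%.
- **A success at the interim is tested at about 2.5%.** True, and the SAP puts interim power at 95.15%. The excess arises only through the second look. But under the null about 97.5% of trials fail at the interim, so the second look is nearly always taken.

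**Conclusion.** The concern holds. With 97.5% at both looks the overall one-sided type I error is about 3% to 4%: 2.80% to 3.85% from the SAP's own tables, and about 3.3% to 3.7% in the larger re-simulations. That is roughly 1.3 to 1.5 times the stated 2.5%, and each look taken alone is close to nominal. The conclusion rests on reading the Final type I rows as increments and, for the re-simulation, on assumed stratum event rates. The error stayed above 2.5% under both rate assumptions. The exact size, and so the exact replacement threshold, depends on those rates and on the information available at the interim.

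**What to change.** Amend the SAP before the formal interim analysis so that ξ is chosen to keep P(success at interim or final) at or below 2.5% when the true difference is 8.0 points, in every tabulated scenario. Two starting points:

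- **One threshold at both looks.** About 98.2% to 98.4% gives close to 2.5%; 98.5% is slightly conservative (2.0% to 2.5%).
- **A Pocock-type pair matching the sample size calculation.** For 70% information, about 98.0% at the interim and 98.8% at the final. Because the interim model holds more information than that, the pair should come out at about 2.2% to 2.4%.

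Confirm with at least 20,000 trials per scenario: the Monte Carlo standard error is √(0.025 × 0.975 / 20,000) = 0.11 points, against 0.35 with 2,000. State the stratum event rates used. Add a cumulative type I error row to Tables 5 and 6, label what Final means, and put the power table on the same basis. If 97.5% must stay, state the overall one-sided alpha as about 3% to 4% wherever 0.025 is claimed.

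The cost is an amendment and a re-run of existing code. Power falls by about 1 to 2 points (in one Gamma-draw scenario, cumulative power went from 96.9% at 97.5% to 95.1% at 98.5%) and stays above the stated 90%. No extra patients are needed.
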